#### 9.1.1 Severity

Severity of an AE is defined as a qualitative assessment of the degree of intensity of an AE as determined by the investigator or reported to him/her by the subject. The assessment of severity is made irrespective of relationship to IP or seriousness of the event and should be evaluated according to the following scale:

- **Mild:** Event is noticeable to the subject, but is easily tolerated and does not interfere with the subject's daily activities.
- **Moderate:** Event is bothersome, possibly requiring additional therapy, and may interfere with the subject's daily activities.
- **Severe:** Event is intolerable, necessitates additional therapy or alteration of therapy, and interferes with the subject's daily activities.

#### 9.1.2 Relationship to Investigational Product

The relationship of each AE to the IP should be determined by the investigator using these explanations:

- **Suspected:** A reasonable possibility exists that the IP caused the AE. A suspected AE can be further defined as:

- *Definite*: Relationship exists when the AE follows a reasonable sequence from the time of IP administration, follows a known response pattern of the drug class, is confirmed by improvement on stopping the IP and no other reasonable cause exists.
- *Probable*: Relationship exists when the AE follows a reasonable sequence from the time of IP administration, follows a known response pattern of the drug class, is confirmed by improvement on stopping the IP and the suspect IP is the most likely of all causes.
- *Possible*: Relationship exists when the AE follows a reasonable sequence from the time of IP administration, but could also have been produced by the subject's clinical state or by other drugs administered to the subject.
- **Not Suspected**: A reasonable possibility does not exist that the IP caused the AE.
  - *Not Related*: Concurrent illness, concurrent medication, or other known cause is clearly responsible for the AE, the administration of the IP and the occurrence of the AE are not reasonably related in time, OR exposure to IP has not occurred.

Suspected adverse reaction means any AE for which there is a reasonable possibility that the IP caused the AE. "Reasonable possibility" means there is evidence to suggest a causal relationship between the IP and the AE. Types of evidence that would suggest a causal relationship between the IP and the AE event include: a single occurrence of an event that is uncommon and known to be strongly associated with IP exposure (e.g., angioedema, hepatic injury, Stevens-Johnson Syndrome); one or more occurrences of an event that is not commonly associated with IP exposure, but is otherwise uncommon in the population exposed to the IP (e.g., tendon rupture); an aggregate analysis of specific events observed in a clinical trial (such as known consequences of the underlying disease or condition under investigation or other events that commonly occur in the study population independent of drug therapy) that indicates those events occur more frequently in the IP-treatment group than in a concurrent or historical control group.

#### 9.1.3 Expectedness

The expectedness of an AE should be determined based upon existing safety information about the IP using these explanations:

- **Unexpected**: An AE that is not listed in the Investigator's Brochure (IB) or is not listed at the specificity or severity that has been observed.
- **Expected**: An AE that is listed in the IB at the specificity and severity that has been observed.
- **Not applicable**: An AE unrelated to the IP.

AE events that are mentioned in the IB as occurring with a class of products or as anticipated from the pharmacological/mechanical (or other) properties of the product, but are not specifically mentioned as occurring with the particular product under investigation are to be considered unexpected.

The investigator should initially classify the expectedness of an AE, but the final classification is subject to the Medical Monitor's determination.

## 9.2 Serious Adverse Events

An AE is considered serious if, in the view of the investigator, it results in any of the following outcomes:

- Death;
- A life-threatening AE;

Note: An AE is considered "life-threatening" if, in the view of the investigator its occurrence places the subject at immediate risk of death. It does not include an AE that, had it occurred in a more severe form, might have caused death.

- Inpatient hospitalization or prolongation of existing hospitalization;

Note: The term "inpatient hospitalization" refers to any inpatient admission (even if less than 24 hours). For chronic or long-term inpatients, inpatient admission includes transfer within the hospital to an acute/intensive care inpatient unit. Inpatient hospitalization does not include: emergency room visits; outpatient/same-day/ambulatory procedures; observation/short stay units; rehabilitation facilities; hospice facilities; nursing homes; or clinical research/phase 1 units.

Note: The term "prolongation of existing hospitalization" refers to any extension of an inpatient hospitalization beyond the stay anticipated or required for the reason for the initial admission as determined by the investigator or treating physician.

- A persistent or significant incapacity or substantial disruption of the ability to conduct normal life functions;

Note: A serious adverse event (SAE) specifically related to visual threat would be interpreted as any potential impairment or damage to the subject's eyes (e.g., hemorrhage, retinal detachment, central corneal ulcer or damage to the optic nerve).

- A congenital anomaly/birth defect.

Important medical events that may not result in death, are life-threatening, or require hospitalization may be considered serious when, based upon appropriate medical judgment, they may jeopardize the subject and may require medical or surgical intervention to prevent one of the outcomes listed in this definition.

## 9.3 Procedures for Reporting Adverse Events

All AEs and their outcomes must be reported to Ora and the IRB/IEC as required by the IRB/IEC, federal, state, or local regulations and governing health authorities and recorded on the appropriate CRF. AE's will be collected from first dose of study drug to 30 days after treatment discontinuation.

### **9.3.1 Reporting a Suspected Unexpected Adverse Reaction**

All AEs that are ‘suspected’ and ‘unexpected’ are to be reported to Ora and the IRB/IEC as required by the IRB/IEC, federal, state, or local regulations and governing health authorities.

### **9.3.2 Reporting a Serious Adverse Event**

To ensure subject safety, all SAEs, regardless of relationship to the IP, must be immediately reported. All information relevant to the SAE must be recorded on the appropriate CRFs. The investigator is obligated to pursue and obtain information requested by Ora in addition to that information reported on the CRF. All subjects experiencing a SAE must be followed up and the outcome reported.

In the event of a SAE, the investigator must notify Ora immediately; obtain and maintain in his/her files all pertinent medical records, information, and medical judgments from colleagues who assisted in the treatment and follow-up of the subject; provide Ora with a complete case history, which includes a statement as to whether the event was or was not suspected to be related to the use of the IP; and inform the IRB of the SAE within their guidelines for reporting SAEs.

Contact information for reporting SAEs and ADEs:

Clinical Project Manager: [name]	
Company:	Ora, Inc.
Office [contact] [name]
Alternative [contact]
Office [contact]

### **9.4 Procedures for Unmasking (if applicable)**

All subjects, investigators, and study personnel involved with the conduct of the study will be masked with regard to treatment assignments. When medically necessary, the investigator may need to determine what treatment arm has been assigned to a subject. When possible (i.e., in non-emergent situations), Ora should be notified before unmasking study drug. Ora must be informed immediately about any unmasking event.

If the investigator identifies a medical need for unmasking the treatment assignment of a subject, he should contact Ora prior to unmasking the identity of the IP, if possible. Ora will ask the site to complete and send them the Unmasking Request Form. Ora will

determine if the unmasking request should be granted. The result of the request will be documented on the Unmasking Request Form. If approval is granted to unmask a subject, written permission via the Unmasking Request Form will be provided to the investigator. The investigator will unmask the subject using the unmasking report. The investigator will complete the Unmasking Memo form and include it in the subject's study file and provide a copy for the Trial Master File (TMF). For each unmasked request, the reason, date, signature, and name of the person who unmasked the subject, must be noted in the subject's study file. Unmasked subjects will be discontinued from the study.

### **9.5 Type and Duration of the Follow-up of Subjects after Adverse Events**

The investigator will follow unresolved AEs to resolution until the subject is lost to follow-up or until the AE is otherwise classified. Resolution means the subject has returned to baseline state of health or the investigator does not expect any further improvement or worsening of the AE. If the subject is lost to follow-up, the investigator should make 3 reasonable attempts to contact the subject via telephone, post, or certified mail. All follow-up will be documented in the subject's source document. Non-serious AEs identified on the last scheduled contact must be recorded on the AE CRF with the status noted.

If the investigator becomes aware of any new information regarding an existing SAE (i.e., resolution, change in condition, or new treatment), a new SAE/Unanticipated Report Form must be completed and faxed to Ora within 24 hours of the site's awareness of the new information. The original SAE form is not to be altered. The report should describe whether the event has resolved or continues and how the event was treated.

## **10 STATISTICAL HYPOTHESES AND METHODS OF ANALYSES**

### **10.1 Analysis Populations**

#### Analysis Populations

- Modified Intent-to-Treat Population – The modified intent-to-treat (mITT) population includes all randomized subjects with at least one post visit 2 study assessment. Efficacy analysis will be performed on the mITT population. Subjects in the mITT population will be analyzed as randomized.
- Safety Population – The safety population includes all subjects who have received at least one dose of the investigational product. Subjects in the Safety population will be analyzed as treated.

The statistical analysis of safety data will be performed for the safety population. The analysis of baseline and all efficacy data will be performed for the mITT population.

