## SYNOPSIS

Protocol Title:	A Single-Center, Randomized, Double Masked, Placebo Controlled Clinical Study to Assess the Safety and Efficacy of Topical Naltrexone Ophthalmic Solution on the Signs and Symptoms of Dry Eye in Diabetic Subjects
Protocol Number:	DDES001
Investigational Product:	1) Naltrexone Ophthalmic Solution, 0.002% 2) Placebo Ophthalmic Solution
Study Phase:	2
Primary Objective(s):	The objective of this exploratory study is to determine the safety and efficacy of 0.002% Naltrexone Ophthalmic Solution, compared to placebo for the treatment of the signs and symptoms of dry eye in diabetic subjects.
Secondary Objective(s):	To assess the tolerability of twice daily administered 0.002% Naltrexone Ophthalmic Solution, eye drops vs placebo
Overall Study Design:	
Structure:	Single-center, double-masked, randomized, placebo-controlled study
Duration:	An individual subject's participation is estimated to be approximately 38 days
Controls:	Placebo (vehicle minus active) Ophthalmic Solution
Dosage/Dose Regimen/ Instillation/Application/Use:	Screening: During a 10-day study run-in period (for the purpose of subject selection) prior to randomization, all subjects will receive Placebo Ophthalmic Solution (Vehicle) bilaterally BID Subjects eligible to be randomized will receive one of the following treatments to be administered bilaterally BID for 29 days (from Visit 2 to Visit 5).

	1) Naltrexone Ophthalmic Solution, 0.002% 2) Placebo Ophthalmic Solution (Vehicle)
Summary of Visit Schedule:	5 visits over the course of approximately 6 weeks: 

• Visit 1 = Day <math>-10 \pm 1</math>, Screening

• Visit 2 = Day 1, Confirmation / Baseline

• Visit 3 = Day <math>8 \pm 1</math>, One Week Follow-Up

• Visit 4 = Day <math>15 \pm 1</math>, Two Week Follow-Up

• Visit 5 = Day <math>29 \pm 2</math>, Four Week Follow-Up and Study Exit

Measures Taken to Reduce Bias:	This is a randomized treatment assignment, double masked study.
Study Population Characteristics:	
Number of Subjects:	60 (30 per treatment arm) subjects
Condition/Disease:	Diabetic subjects with Dry Eye Syndrome

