## 4 OVERALL STUDY DESIGN

This is a Phase 2, single-center, double-masked, randomized, placebo-controlled study to compare the safety and efficacy of Naltrexone Ophthalmic Solution, 0.002% to placebo for the treatment of the signs and symptoms of dry eye in diabetic subjects. Subjects eligible to be randomized will receive one of the following treatments to be administered bilaterally BID for 29 days (from Visit 2 to Visit 5): Naltrexone Ophthalmic Solution, 0.002% or Placebo Ophthalmic Solution (Vehicle). During a 10-day study run-in period (for the purpose of subject selection) prior to randomization, all subjects will receive Placebo Ophthalmic Solution (Vehicle) bilaterally BID. Participants who terminate early during the application period will be asked to complete safety assessments (if the participants agree) prior to study exit. Participants who are terminated early from the study will not be replaced. A chart illustrating the study's structure is below.

Visit 1 Day $-10 \pm 1$ day Screening	

• Informed consent/Health Information Portability and Accountability Act (HIPAA) consent

• Demographic data, medical/medication, and ocular history

• Urine Pregnancy Test (if applicable)

• Ocular Surface Disease Index (OSDI)

• Ora Calibra® Ocular Discomfort Scale

• Ora Calibra® Ocular Discomfort & 4-Symptom Questionnaire

• VAS

• Best Corrected Visual Acuity (BCVA)

• Slit lamp biomicroscopy

• Ora Calibra® Conjunctival redness;

• Corneal sensitivity (Cochet-Bonnet)

• TFBUT;

--	--

	

• Fluorescein staining (Ora Calibra® scale); regions: central, superior, inferior, temporal, nasal, corneal sum, conjunctival sum, and total eye score

• Lissamine green staining (Ora Calibra® scale); regions: inferior, superior, central, temporal, nasal, corneal sum, conjunctival sum, and total eye score)

• Review inclusion and exclusion criteria

• Run-in (vehicle) dose

• Dispense vehicle to all qualifying patients for BID dosing until Visit 2

• Dispense dosing diary

• Adverse Event Query

• Schedule Visit 2

	↓
	Approximate 10-Day Run-In Period with Vehicle

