## 5 STUDY POPULATION

### 5.1 Number of Subjects (approximate)

Approximately 60 (30 per treatment arm) subjects will be enrolled in the study. The total number of expected participants, including screen failures, is approximately 120.

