## 10.3 Sample Size

The study is not powered to show statistical differences for any of the efficacy endpoints. The sample size was determined based on prior clinical trial experience with in subjects with dry eye syndrome and is deemed to be robust sufficient to

evaluate the safety and tolerability of Naltrexone Ophthalmic Solution in this population and to gather efficacy data that will aid in powering future clinical trials.

With a sample size of 60 subjects in the Safety and Efficacy Assessment, the study will have 79% probability of detecting AEs occurring at a rate of 5% or more in either treatment arm.

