## 13 APPENDICES

### APPENDIX 1: SCHEDULE OF VISITS AND MEASUREMENTS

Procedure	Visit 1 Day-10 ±1	Visit 2 Day 1	Visit 3 Day 8 ± 1	Visit 4 Day 15 ± 1	Visit 5 Day 29 ±2
Informed Consent	X				
Demographic Data	X				
Medical/Medication History	X				
Medical/Medication History Update		X	X	X	X
Randomization		X			
Urine pregnancy test	X				X
OSDI ® questionnaire	X	X	X	X	X
Ora Calibra ® Ocular Discomfort Scale	X	X	X	X	X
Ora Calibra ® Ocular Discomfort & 4 Symptom Questionnaire	X	X	X	X	X
Visual Acuity Scale (VAS)	X	X	X	X	X
BCVA	X	X	X	X	X
Slit lamp biomicroscopy	X	X	X	X	X
Ora Calibra ® Conjunctival redness	X	X	X	X	X
Corneal Sensitivity (Cochet-Bonnet)	X	X	X	X	X
Tear Osmolarity		X			X
InflammaDry ® (MMP-9) testing		X			X
TFBUT	X	X	X	X	X

Corneal and conjunctival fluorescein staining	X	X	X	X	X
Corneal and conjunctival lissamine green staining	X	X	X	X	X
Schirmer's Test		X	X	X	X
IOP		X			X
Dilated Fundoscopy		X			X
ENK blood draw (optional)					X
Review Eligibility Criteria	X	X	X	X	X
Run-in (vehicle) instillation at study site	X				
Study drug/placebo instillation at study site		X	X	X	X
Run-in (vehicle) Dispensed	X				
Run-in (vehicle) Returned		X			
Adverse Event Query	X	X	X	X	X
Investigational Product Dispensed		X	X	X	
Investigational Product Returned			X	X	X
Dosing Diary Dispensed	X	X	X	X	
Exit from Study					X

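### Does the Safety population let subjects who were dosed in the run-in but never randomized into the placebo denominator?

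*Combined protocol and SAP*

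**What the plan says.** Section 10.1 (repeated in the Synopsis) defines two analysis sets. For safety: "The safety population includes all subjects who have received at least one dose of the investigational product", analyzed as treated. The mITT population beside it "includes all randomized subjects with at least one post visit 2 study assessment". Only the second definition mentions randomization.

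The Synopsis row for investigational product reads "1) Naltrexone Ophthalmic Solution, 0.002% 2) Placebo Ophthalmic Solution". Section 4 says that, during a 10-day run-in used for selection, "prior to randomization, all subjects will receive Placebo Ophthalmic Solution (Vehicle) bilaterally BID". Section 8.1.5 assigns the randomization number at the end of Visit 2, after eligibility has been checked again. On numbers, Section 5.1 plans about 60 randomized subjects, 30 per arm, and adds: "The total number of expected participants, including screen failures, is approximately 120".

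Section 10.4.5 calls an adverse event treatment-emergent if it starts or worsens after the first dose of study treatment. Section 10.3 claims a "79% probability of detecting AEs occurring at a rate of 5% or more in either treatment arm".

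**The concern.** Taken literally, the definitions chain together. Placebo is an investigational product and the run-in drop is placebo, so one run-in dose meets the Safety definition. The as-treated rule would then put a Visit 2 failure in the placebo column. Such failures are to be expected, because the staining criterion, and the lissamine green or OSDI criterion, must be met at both visits.

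If treatment-emergent events are counted from Visit 2, each such subject would add one to the placebo denominator and could never add an event. Any nonzero placebo percentage would fall while the naltrexone percentage stayed put, so naltrexone would look relatively worse. Event percentages by group are a core safety output, and event detection is the only calculation offered for the sample size.

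**Working it through.** **1. The plan's own figure.** The probability of seeing at least one event at rate p among n subjects is 1 − (1 − p)^n, with p = 0.05 from Section 10.3.

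- n = 30: 1 − 0.95^30 = 78.5%, the stated 79%.
- n = 60: 1 − 0.95^60 = 95.4%, which does not match.

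The safety planning therefore rests on 30 subjects in an arm, the randomized number. A placebo arm enlarged by run-in failures would give another figure: 90.1% at n = 45, for example.

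**2. How the documents use the terms.**

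- Appendix 1 has a row "Run-in (vehicle) Dispensed" marked at Visit 1 and a separate row "Investigational Product Dispensed" marked at Visits 2 to 4. Return of product and on-site instillation are split in the same way.
- Section 7.1.3(c) contrasts one bottle of run-in with two study drug bottles for Visits 2 to 5.
- Section 11.5.1 describes the run-in bottle apart from the kits of investigational drug.
- Section 11.5.2 limits the investigational product to subjects entered into the study. Section 8.1.4 makes final entry depend on all criteria, some of which are tested at Visit 2. Entered is not formally defined, so this supports the narrow reading without settling it.
- Section 10.4.1 takes baseline as the last value before study treatment starts, usually Visit 2, and presents every summary by treatment group. A subject who was never randomized has no assigned group.

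**3. What a wrong reading would cost.** Let k be the number of dosed run-in failures. The documents do not give it. It lies between 0 and 120 − 60 = 60, and 60 would require that nobody failed at Visit 1. Assume 3 of 30 randomized placebo subjects have a treatment-emergent event, and that naltrexone has the same underlying rate.

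*Both terms read naturally* (investigational product and study treatment both start at Visit 2): placebo is 3/30 = 10.0%. Nothing changes.

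*Investigational product read literally, study treatment read naturally:* placebo is 3/(30 + k).

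| k | Placebo | Fall from 10.0% |
|---|---|---|
| 6 | 3/36 = 8.3% | 1.7 points |
| 15 | 3/45 = 6.7% | 3.3 points |
| 30 | 3/60 = 5.0% | 5.0 points |
| 60 | 3/90 = 3.3% | 6.7 points |

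For scale, one subject in 30 is 3.3 points.

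*Both read literally:* run-in events count for everyone, including the run-in days of randomized subjects. At a constant daily rate, 10% over 29 days becomes 1 − 0.9^(39/29) = 13.2% over 39 days, or 3.96 of 30. A failure with 10 days of exposure has 1 − 0.9^(10/29) = 3.57%. Placebo is then (3.96 + 0.0357k)/(30 + k) = 11.6%, 10.0%, 8.4% and 6.8% for k = 6, 15, 30 and 60, against 13.2% for naltrexone. Some relative dilution remains, but it arises from mixing 10-day with 39-day exposure, which would be plain from the denominators.

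**The case for a change.** The strongest reply is that signs of intent do not amend a definition. The word randomized stands in one bullet and is missing from the next. Placebo appears as investigational product in the Synopsis and again under Study Treatment in Section 7.1.1. The terms are also used loosely: Section 8.3.1 calls the bottle returned at Visit 2 study drug, Section 8.5 has study drug instruction at Visit 1, and Section 9.3 starts event collection at the first dose of study drug. Section 10 further mentions a Comfort Assessment and a PP population that the protocol never defines, so its wording may not have been tailored to this design.

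Part of this stands: the text does not expressly exclude run-in-only subjects. The loose usage, however, carries little weight. The same Visit 2 return is called run-in in the Section 4 chart and in Appendix 1. Section 8.5 speaks of collecting study drug from Visit 1, before any has been dispensed. These are labels for bottles, and study drug is not the term in the Safety definition. The one-directional dilution also needs investigational product read literally and study treatment read naturally in the same analysis, and nothing in the plan invites that combination.

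**Conclusion.** No change is needed. The Safety definition leaves a word unsaid, and an analyst would supply it from the schedule, the baseline definition and the 30-per-arm basis of the 79%. A placebo column far larger than the naltrexone column, in a 1:1 trial of 60, would be noticed at once. Section 10.4.6 already commits to a full SAP before database lock and unmasking, where such operational definitions are normally spelled out.

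The possible distortion ranges from nothing to a fall from 10.0% to 3.3% in the placebo percentage. That range rests on an assumed 3/30 event rate, an unknown k, an upper bound that needs no Visit 1 failures, and the mixed reading of the two terms. On the natural reading the effect is zero. The safety summaries are descriptive, so no hypothesis test, error rate or planned figure is affected.
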